5.7.2.4 Supplementary Analysis

Not applicable.

5.7.2.5 Subgroup Analysis

No subgroup analyses will be performed.

5.7.3 Analysis of Key Secondary Efficacy Endpoints

5.7.3.1 Endpoint, Treatment Effect and Estimand Definition

The secondary efficacy variable is the percent change in PSA from baseline (prior to injection) measured at Week 12 and Week 24. Percent change in PSA is defined as the value of difference between the PSA values at Week 12 and Week 24 and the baseline value divided by the baseline value.

$$\text{Percent change from baseline (\%)} = \left(\frac{\text{PSA value at Week 12 or Week 24} - \text{Baseline value}}{\text{Baseline value}} \right) \times 100$$

5.7.3.2 *Main Secondary Analysis*

PSA percent change from Baseline will be reported at each subsequent visit, using descriptive statistics on the FAS and PPS.

Observed value will also be summarized for the FAS. Descriptive statistics to be presented include number of available observations (n), mean, median, SD, minimum, maximum, standard error mean (SEM, calculated as SD divided by the square root of n), coefficient of variation (CV) and 95% CI for mean.

Individual PSA level data versus visit will be plotted by participant on a semi-logarithmic scale on the FAS. The arithmetic mean (\pm SD) PSA levels versus visit will also be provided.

All PSA data will be listed by participant and timepoint on all participants enrolled.

5.7.3.3 *Subgroup Analysis*

No subgroup analyses will be performed.

5.7.4 *Analysis of Other Secondary Efficacy Endpoints*

Not applicable.

5.7.5 *Analysis of Exploratory Endpoints*

An exploratory endpoint is defined in Protocol, but the analysis details will be described in a separate data analysis plan.

5.8 Safety

5.8.1 *General Consideration*

All safety summaries and analyses will be based upon the Safety Set. All safety data will be included in participant data listings (see listing detail conventions in Appendix A4). This is a single-arm study, and there will be no statistical comparison between the treatment groups for safety data.

Haematological and biochemical toxicities will be recorded and graded according to the National Cancer Institute-Common Toxicity Criteria for Adverse Events (NCI-CTCAE) version 5.0 or higher, where available (refer to appendix A5 for grading using NCI-CTCAE 5.0). The NCI-CTCAE Grade 3 and 4 haematology and biochemistry variables by participant and by visit will be listed.

5.8.2 *Extent of Exposure*

Summary of the actual dose and duration of exposure will be provided on the Safety Set. Actual dose will be calculated as planned dose (22.5 mg) multiplied by (1 - percentage of residual in syringe). The definition of the duration of exposure is from first IMP administration to the date of end of study. Participant's exposure data will be listed on the Safety Set.

5.8.3 *Adverse Event*

All adverse events (AEs) recorded in the eCRF will be coded using the latest version of MedDRA dictionary in effect within IPSEN at the time of the database lock. AEs will be classified as Treatment-Emergent AEs (TEAEs) according to the rules below:

- Events with start date on or after the date of IMP administration and up to 24 weeks after date of first dose of treatment.
- Events whose severity (measured by National Cancer Institute – Common Toxicity Criteria (NCI-CTCAE) Version 5.0 grading) worsens on or after the date of IMP administration,

Refer to appendix ‘

[Partial/Missing Date Convention](#)’ for handling of partial date.

In the case where it is not possible to define an AE as treatment emergent or not, the AE will be classified by the most conservative case; i.e. treatment emergent.

In addition, if severity of an AE changes during the study, a separate AE will be recorded for each severity on the AE eCRF. The “first” and subsequent AEs will be identified based on the AE start date or the severity change date. If “first” AE record occurs before dosing, and subsequent AEs occur on or after dosing, subsequent AEs whose severity worsens compared with the severity of “first” AE record will be classified as TEAE. If “first” AE record occurs on or after dosing, “first” AE record and subsequent AEs will be classified as TEAE.

The AE summaries include the following summaries:

- An overview table summarizing the
 - number and percentage of participants with at least one of the following AEs: any AE; any TEAE; any severe TEAE (CTCAE grade ≥ 3); treatment-related TEAE; TEAE leading to discontinuation from the study, Serious Adverse Event (SAE), treatment emergent SAE, treatment-related SAE, treatment emergent SAE leading to death, treatment-related SAE leading to death, treatment emergent SAE leading to discontinuation from the study, most frequent TEAEs ($>5\%$), death,
 - corresponding number of events for each of the AE categories listed above
- A summary of the number and percentage of participants reporting a TEAE by treatment group, SOC and PT,
- A summary of the number and percentage of participants reporting a TEAE by treatment group and PT,
- A summary of the number and percentage of participants reporting a TEAE by treatment group, maximum CTCAE grade, SOC and PT,
- A summary of the number and percentage of participants reporting a TEAE by treatment group, maximum causality, SOC and PT,
- A summary of the number and percentage of participants reporting a treatment-related TEAE by treatment group, maximum CTCAE grade, SOC and PT,
- A summary of the number and percentage of participants reporting a most frequent TEAE ($>5\%$) by treatment group and PT,
- A summary of the number and percentage of participants reporting a non-serious TEAE by treatment group, SOC and PT.

AEs summaries will be ordered in term of decreasing frequency for SOC and PT within SOC in the treatment group, and then alphabetically for SOC and PT within SOC if ties. AEs summaries by PT will be ordered in term of decreasing frequency of PT in the treatment group and then alphabetically for PT if ties.

AEs will be counted as follows:

- Participants with more than one AE within a particular SOC are counted only once for that SOC. Similarly, participants with more than one AE within a particular PT are counted only once for that PT;
- Participants reporting a TEAE more than once within that SOC/ PT, the TEAE with the worst-case grade (grade order: 5>4>3>2>1>missing) will be used in the corresponding grade summaries;

- Participants reporting a TEAE more than once within that SOC/ PT, the TEAE with the worst-case relationship to study medication (order: related > not related > missing) will be used in the corresponding relationship summaries;
- If the grade is missing for a TEAE, it will be considered as missing in the summary tables;
- Summary by grade will be presented;
- If the causality is missing for a TEAE, it will be considered related in the summary tables;
- The non-serious TEAEs table should include a specific row “any non-serious TEAE above 5%”.

In addition, a listing with all AEs data will be listed by treatment group including non-TEAEs, Treatment-emergence status will be flagged in the listing.

Deaths, SAEs, and Other Significant Adverse Events

The following summaries will be provided:

- A summary of the number and percentage of participants reporting a SAE by treatment group, SOC and PT,
- A summary of the number and percentage of participants reporting a treatment emergent SAE by treatment group, SOC and PT,
- A summary of the number and percentage of participants reporting a treatment-related SAE by treatment group, SOC and PT,
- A summary of the number and percentage of participants reporting a SAE by treatment group, maximum CTCAE grade, SOC and PT,
- A summary of the number and percentage of participants reporting a SAE by treatment group, maximum causality, SOC and PT,
- A summary of the number and percentage of participants with TEAEs leading to discontinuation of study by treatment group, SOC and PT,
- A summary of the number and percentage of deaths (including SAEs with fatal outcome and deaths as PT) including primary reasons for death.

AEs of special interest is not applicable.

The following listings will be provided:

- A listing of all deaths that occurred during the study,
- A listing of all SAEs.
- A listing of TEAEs leading to discontinuation of study.

5.8.4 *Laboratory Data*

All laboratory data (Hematology and Clinical Chemistry) will be presented in the units of International System of Units (SI).

The following summaries will be provided:

- A summary of the actual and change from baseline in each laboratory parameter by treatment group and visit,
- A shift from baseline to each post-baseline timepoints of the number and percentage of participants experiencing low, normal or high values, by laboratory parameter,
- A shift from baseline to end of study according to Common Toxicity (CTC) grading system (Version 5.0 or higher),

For shift tables, the denominator should be the number of participants with both a baseline and a post-baseline assessment at a given timepoint.

In addition, the following listings are to be provided:

- A listing of all laboratory data. Out-of-reference-range values will be flagged as high (H) or low (L),
- A listing of all abnormal data.
- A listing of CTCAE grade 3 and higher values. All data for a laboratory parameter will be displayed for a participant who has any post-baseline value with CTCAE grade greater than or equal to 3 for the parameter.

5.8.5 ***Vital Signs***

Blood pressure, temperature, respiratory rate and heart rate will be assessed. Any clinically significant vital signs will be recorded as AEs. The following summaries are to be provided:

- A summary of the actual and change from baseline in each vital sign parameter by treatment group and visit,
- A shift from baseline to post-dose in interpretation of clinical significance (normal, abnormal, not clinically significant [NCS], abnormal, clinically significant [CS]).

The following listing are to be provided:

- A listing of vital sign data.
- Listing of all abnormal data.

5.8.6 ***Electrocardiogram (ECG)***

Results from the local lab units will be used.

The following quantitative ECG measurements will be taken during the study:

- heart rate (bpm),
- RR interval (msec),
- PR interval (msec),
- QRS interval (msec),
- QT interval (msec),

Fridericia corrected QT (QTcF) interval (msec) = $QT/\sqrt[3]{RR}$;

An overall Investigator assessment of ECG will be provided as “normal”, “abnormal NCS” and “abnormal CS”. Any clinically significant abnormalities will be recorded as AEs.

The following summaries of ECG data may be appropriate:

- A summary of the actual and change from baseline in each ECG parameter by treatment group and visit,
- A shift from baseline (normal vs. abnormal NCS vs. abnormal CS) to each post-baseline visit.

The following listing are to be provided:

- A listing of ECG data.
- A listing of all abnormal data.

5.8.7 ***Physical Examination***

The following summary and listings will be provided:

- A shift from baseline (normal vs abnormal NCS vs. abnormal CS) to each post-baseline visit by body system.
- A listing with any participants with at least one physical examination abnormality.

5.8.8 *Other*

Local tolerance will be assessed 2 hours (± 15 minutes) after the single injection of 6-month formulation triptorelin, the injection site will be examined including but not limited to tenderness, erythema, swelling, haematoma, rash, pain, itching and induration. The presence of local tolerance will be listed and summarized for each symptom. The maximum length (mm) and width (mm) of presented symptom will also be summarized where applicable.

5.9 PK

5.9.1 *Triptorelin Plasma Concentrations*

Tables, listings and figures of triptorelin plasma concentrations will be generated by the SP for both the Rich PK Analysis Set and the Population PK Analysis Set.

Individual plasma concentrations of triptorelin will be listed and summarised by visit and time points using descriptive statistics for continuous variables including number of available observations (n), mean, median, SD, minimum, maximum, SEM, CV, geometric mean, geometric coefficient of variation (gCV) % (assuming log normally distributed data, and calculated as: $gCV\% = \text{SQRT}(e^{s^2}-1)*100$; where s is the SD of the log-transformed values) and 95% CI for mean.

Plasma concentrations should be displayed with the same precision than the LLOQ. In descriptive statistics, calculations derived from plasma concentrations (mean, minimum, maximum, median, SD etc.) should follow the same rule whereas CV% will only be displayed with one decimal digit.

Source data as reported from the laboratory will be used for calculation of concentration summary statistics. All values below or above a limit of detection (e.g. <0.1 or >100) will be listed as such. LLOQ will be presented as 'BLQ' in the listings and the LLOQ value presented as a footnote. Missing PK samples will be reported as no sample (NS) and/or not reportable (NR) and considered excluded from plasma concentration summary statistics. For summary tables, all BLQs will be considered as missing and will not be included in the summary statistics. The number of BLQs and non-BLQs at each scheduled time point will be reported. Summary Statistics will not be calculated if non-BLQ concentrations at a scheduled time point is less than 3 and if more than one third (1 out of every 3 values) are missing; in that case only minimum and maximum will be reported. Individual and mean triptorelin concentration time profiles, as well as spaghetti plots, will be generated.

5.9.2 *Triptorelin PK Analysis*

The PK analysis of triptorelin plasma concentrations for the rich PK Analysis Set will be performed by non-compartmental analysis (NCA). The NCA analysis will be described in a separate data analysis plan and reported in a standalone report. If warranted by the data population pharmacokinetics (PopPK) modelling will be performed on the Population PK Analysis Set using concentrations obtained from all participants in order to describe the pharmacokinetics of triptorelin 6-month formulation in the prostate cancer population. Population PK analysis will be described in a separate data analysis plan and presented in a standalone report.

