6M=6-month formulation, AE=adverse event, ALT=alanine aminotransaminase, AST=aspartate aminotransaminase, CRF=case report form, D=day; ECG=electrocardiography; ECOG=Eastern Cooperative Oncology Group, EoS/EW=end of study/early withdrawal, Hb=haemoglobin, M1b=distant metastasis bone(s), MRI=magnetic resonance imaging; PD=pharmacodynamic, PK=pharmacokinetics, PSA=prostate-specific antigen, WBC=white blood cell.

-
- a Assessment or blood sampling to be performed prior to study intervention injection. PK Predose sampling window (\leq 30 minutes).
 - b ECG to be assessed as clinically indicated at any other time in the study as required.
 - c Haematology (WBC, platelet count, Hb), Blood Chemistry (creatinine, glucose, ALT, AST, alkaline phosphatase, bilirubin (total and conjugated)) will be tested at the local laboratory. Glucose: fasting levels in all participants at Screening visit, fasting levels on Days 1 and 169. Fasting is not necessary for diabetic participants.
 - d Injection site to be specifically checked 2 hours \pm 15 minutes after injection for local reactions on Day 1. After Day 1, any local reaction AE to be collected on the CRF in the same manner as other AEs.
 - e Measurement of testosterone, PSA and laboratory safety tests for analysis purposes only and not for eligibility. The screening testosterone, PSA and safety laboratory test results will be used for eligibility.
 - f Complete physical examination to be performed (or brief physical examination based on investigator judgement). Participants, particularly those with M1b status, should be advised regarding clinical signs suggestive of spinal cord compression.
 - g Scan for prostate gland or the whole body, only if necessary, based on investigator's judgement. An MRI scan is not required if performed within 1 month of screening.
 - h Testosterone and PSA testing will be performed at the central laboratory.

See Appendix [10.5](#) for ECOG performance scale.

Table 2 Schedule of Assessments for the Pharmacokinetic/Pharmacodynamic Subset of Participants

Procedures	Screening	Intervention Period												EoS/EW
		-	-	-	-	-	-	-	Week 4	Week 8	Week 12	Week 16	Week 20	
End of Week	-	-	-	-	-	-	-	-						
Day	D-28 to D-1	D1	D2	D3	D5	D8	D15	D22	D29	D57	D85	D113	D141	D169
Visit Window										±3 days				
Previous (excluding disease-specific) and concomitant medication	X	X	X	X	X	X	X	X	X	X	X	X	X	X
Adverse events	X	X	X	X	X	X	X	X	X	X	X	X	X	X

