9.4.5 Safety Analyses

Safety endpoints are indicated in Section 3.

All safety data will be included in the participant data listings. Analyses and summary tables will be based upon the safety set.

All AEs will be coded according to the Medical Dictionary for Regulatory Activities (MedDRA) version 24.1 (or higher if available) and will be classified by MedDRA preferred term and system organ class. Adverse event listings will be presented by participant, system organ class and PT.

The incidence of all TEAEs and SAEs will be tabulated overall. In addition, summary tables will be presented by maximum intensity and drug relationship.

A TEAE is defined as any AE that occurs during the active phase of the study (from study intervention injection to 24 weeks after injection) if it was not present prior to receiving study intervention, or:

- it was present prior to receiving IMP but the intensity increased during the active phase of the study.
- It became serious during the active phase of the study
- It was present prior to receiving the study intervention and the intensity was the same, but the causality changed to 'related to treatment' during the active phase of the study.

All TEAEs will be flagged in the AEs listings.

Haematological and biochemical toxicities will be recorded and graded according to the NCI CTCAE criteria, where available. The National Cancer Institute-Common Toxicity Criteria for Adverse Events (NCI-CTCAE) Grade 3 and 4 haematology and biochemistry variables by participant and by cycle will be listed.

Actual values and changes from baseline in clinical laboratory tests, physical examinations, vital signs and 12-lead ECG will be summarized using descriptive statistics at each visit. For laboratory data, abnormal values will be flagged in the data listings and a list of clinically significant abnormal values will be presented. Shift tables using the worst on-treatment grade will be presented for the number and percentage of participants with NCI-CTCAE grades.

AEs reported by investigators using the NCI-CTCAE classification (Version 5.0 or higher) will be coded using MedDRA Version 24.1 (or higher if available).

Summary incidence tables will be provided, classified by SOC, PT and associated NCI/CTC worst grade. In the event of multiple occurrences of the same AEs being reported by the same participant, the maximum intensity (Grade 5 >Grade 4 >Grade 3 >Grade 2 >Grade 1 >missing >not applicable) will be chosen.

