5.1 General Considerations

All statistical analyses will be performed using the Statistical Analysis System® software version 9.4 (or higher if available).

5.1.1 *Outputs Presentation*

5.1.1.1 *Tables Header*

Depending on the type of data, the summary tables will be presented as follows:

- For disposition, demographic and baseline data: by treatment group,
- For efficacy and safety data: by treatment group.

5.1.1.2 *Presentation of Treatment Group*

Tables, Figures and Listings (TFLs) will be displayed using the following treatment group label:
Triptorelin 6M

5.1.1.3 *Presentation of Visits / Timepoints*

Summaries by visit will be presented using visit number as collected in the Electronic Case Report Form (eCRF).

Visits in the TFLs will be presented as follows and in the following order:

Long Visit Name	Short Name
Screening	Scr
Baseline	Bsl
Day 1	D1
Day 2	D2
Day 3	D3
Day 5	D5
Day 8	D8
Day 15	D15
Day 22	D22
Week 4 Day 29	W4D29
Week 8 Day57	W8D57
Week 12 Day85	W12D85
Week 16 Day113	W16D113
Week 20 Day141	W20D141
End of Study/Early Withdrawal	EoS/EW

In the event a participant is enrolled, but does not receive study intervention, the participant will not remain in the study and EoS/EW assessment will not be performed.

5.1.2 *Descriptive Statistics*

All raw and derived variables will be listed and described using summary statistics. For categorical variables, summary statistics will be displayed using descriptive statistics by frequency count and percentages by category. The missing category will be presented if there is at least one missing category for at least one treatment group. Except otherwise specified, participants with missing data will be included in the calculation of percentages. For quantitative variables, summary statistics will be displayed using descriptive statistics by number of observations, mean, standard deviation (SD), median, minimum and maximum. Frequency and proportion of missing data will be displayed.

5.1.3 *Baseline Value*

Unless otherwise specified, baseline is defined as the last non-missing measurement taken prior to first Investigational Medicinal Product (IMP) administration (including unscheduled assessments).

5.1.4 *Reference Start Date and Study Day*

Reference start date is defined as the day of the first IMP administration.

The day of the first IMP administration will be Day 1. Study day will be calculated as:

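### The SAP flags treatment-emergent events by calendar date, so a new adverse event found before the injection on Day 1 counts as treatment-emergent, contrary to the protocol

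*SAP*

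**What the plan says.** SAP 5.8.3 has two routes to treatment-emergent status. The first is "Events with start date on or after the date of IMP administration", with an upper limit of 24 weeks from dosing. The second covers events whose CTCAE severity "worsens on or after the date of IMP administration". Both compare dates. The algorithm in SAP Appendix A2 also works on dates, with no clock time. Where status cannot be decided, SAP 5.8.3 says that "the AE will be classified by the most conservative case; i.e. treatment emergent".

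Protocol 9.4.5 defines the active phase as running "from study intervention injection to 24 weeks after injection" and requires that the event was not there before the participant received study intervention. An event already present qualifies only if, in the active phase, it intensifies, becomes serious or is newly judged related.

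In Protocol Table 1 the Day 1 cells for physical examination, vital signs and laboratory safety tests all carry footnote a: "Assessment or blood sampling to be performed prior to study intervention injection". SAP 5.1.3 adds that "baseline is defined as the last non-missing measurement taken prior to first Investigational Medicinal Product (IMP) administration", so these Day 1 values are the baseline whenever they are available.

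SAP 2.6, which lists changes from the protocol's statistical section, has one entry. It concerns the analysis set for medical history and medications, not the TEAE definition.

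**The concern.** Day 1 is the injection date, but the scheduled examination, vital signs and safety bloods of that day come before the injection. A rule that compares dates cannot separate the two halves of the day, so an event that preceded the drug can be reported as having emerged on it. One blood sample could then serve as the baseline in the laboratory shift tables and also produce a treatment-emergent event in the AE tables.

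TEAE incidence is a secondary endpoint, and the study has one arm. In a controlled trial such misclassification would fall on both arms and largely cancel in the comparison; here it goes straight into the reported percentage. The departure is also undeclared, so a reader of the study report would assume that the protocol definition had been applied.

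**Working it through.** **Inputs.** TEAE rules: SAP 5.8.3 and Appendix A2; Protocol 9.4.5. Day 1 timing: Protocol Table 1, footnote a. Baseline: SAP 5.1.3. AE recording: Protocol 8.3.1, 8.3.2, 8.3.5, 8.4.1 and 10.3.1. Planned number: Protocol 9.2 and SAP 2.3.

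**The plan's own figure.** The plan gives no TEAE rate. The only figure used here is the planned number: 165/(1 − 0.15) = 194.1, rounded up to 195. It reproduces.

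**The two rules side by side**, for an event with one onset and no later change:

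| Onset | SAP 5.8.3 (date) | Protocol 9.4.5 (injection) |
|---|---|---|
| Screening, before Day 1 | Not TEAE | Not TEAE |
| Day 1, before injection | **TEAE** | **Not TEAE** |
| Day 1, 2 hours after injection | TEAE | TEAE |

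They differ only in the middle row. The second SAP bullet behaves the same way: a worsening on Day 1 before the injection also counts.

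**What can fall in the middle row.** A finding from a Day 1 pre-dose assessment must pass each of these steps:
1. It is clinically significant (Protocol 8.3.1, 8.3.2, 8.3.5).
2. It is not excluded as an AE under Protocol 10.3.1, for example as an abnormality of the underlying disease no worse than expected, or as ordinary fluctuation of an existing condition.
3. It is new, or newly worse, since screening, which includes the same examination and safety tests up to 28 days earlier.
4. It is recorded as an AE. Protocol 8.4.1 requires this for occurrences between consent and dosing.
5. Its start date, or date of worsening, is entered as Day 1.

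**Size.** The documents give no frequency for such events. Assume that all 195 are treated. Each man whose only qualifying event is of this kind adds 1/195 to TEAE incidence:
- 1 man: 1/195 = 0.51 percentage points
- 2 men: 2/195 = 1.03
- 5 men: 5/195 = 2.56
- 10 men: 10/195 = 5.13

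The counts of 1 to 10 are illustrations, not estimates. A man who has another TEAE anyway adds nothing to overall incidence, though he may add to a row by system organ class or preferred term.

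The SAP's table of TEAEs above 5% starts at 10 men, because 9/195 = 4.62% and 10/195 = 5.13%. One reclassified man can therefore move a preferred term into that table.

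**The case against.** **The SAP already separates pre-dose from post-dose.** Later in 5.8.3 it distinguishes a first AE record before dosing from records on or after dosing. That points to loose drafting rather than a decision to count pre-dose findings. But the paragraph deals with AEs that have several severity records, and it orders them by date: "The “first” and subsequent AEs will be identified based on the AE start date or the severity change date". It does not override the first bullet for a single record dated Day 1.

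**The error is conservative.** It can only raise TEAE counts and cannot hide a signal. This stands, and it limits the importance of the point. The SAP's conservative default, however, is for events whose status cannot be decided. A finding traceable to a pre-dose assessment can be decided, and Protocol 6.4 has the dosing time recorded.

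**Emergence is not causality.** Investigators judge relatedness separately and take timing into account, so a pre-dose finding should be called unrelated and the treatment-related tables should hardly move. This stands too, except that SAP 5.8.3 counts missing causality as related.

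**The data may not support a finer rule.** The documents do not say whether the AE page records onset time or links an event to the assessment that revealed it. This stands, and the fix must allow for it.

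**A stronger reading that the documents do not support.** A reader might infer that every abnormality in the Day 1 examination or bloods becomes a TEAE. It does not: the five steps above must all be met, and no passage makes the date of detection the AE start date.

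A reader might also reason that Table 1 has two safety draws dated on or after the injection, Day 1 and Day 169, so that 195/(195 + 165) = 54% of scheduled-draw laboratory TEAEs predate the drug. That assumes the same chance of a newly reported abnormality at Day 1, at most 28 days after an untreated screening draw, as 24 weeks after the drug. Nothing supports this. It also leaves out the early-withdrawal draw; if all 195 − 165 = 30 dropouts attended it, the same reasoning gives 195/390 = 50%. Neither share should be used.

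**Conclusion.** The point holds as a definitional mismatch of limited reach. As written, SAP 5.8.3 classes an AE with onset or worsening on Day 1 before the injection as treatment-emergent. Protocol 9.4.5 does not, unless one of its later-change conditions is met, and SAP 2.6 does not disclose the difference. That follows from the text and needs no assumption.

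Its size is unknown and probably small. The figure of 0.51 percentage points per affected man assumes 195 treated and no other TEAE in that man. The direction is upward only. The co-primary testosterone endpoints are untouched. This is a correction worth making, not a threat to the study's conclusions.

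**What to change.** In SAP 5.8.3, align both bullets with Protocol 9.4.5, so that onset or worsening counts when it occurs at or after the injection rather than on or after its date. For AEs dated on the injection day:
- compare onset time with the recorded dosing time where onset time exists;
- otherwise use a before/after-injection flag, or a link to the pre-dose assessment, where available;
- class events known to precede the injection as not treatment-emergent, subject to the protocol's conditions for later change;
- keep the conservative default only where the order cannot be determined.

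Carry the same rule into Appendix A2. If the date rule is kept instead, list it in SAP 2.6 as a departure from the protocol.

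Cost: a small SAP edit and minor programming. If the eCRF lacks onset time, it may also need a query or a tick box, limited to AEs dated Day 1.
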